Due to de-centralized autonomic cardiovascular control and low plasma NE, persons with SCI struggle with circadian BP dysregulation, [78-80] and individuals with spinal cord lesions above T5 tend to be persistently hypotensive [79-84] with frequent episodes of OH. [1, 85-88] Although many of these individuals remain asymptomatic [89-91], mounting evidence suggests adverse cardiac, [92, 93] cerebral [10, 11, 94] and cognitive consequences. [7] Further, it has been suggested that the superimposition of hypotension and cognitive impairment on the physical, social and emotional limitations already experienced by many individuals with SCI can adversely impact autonomy, social independence and quality of life (QOL) [18, 95, 96]. While we appreciate that the asymptomatic nature of hypotension and OH often precludes clinical intervention, wide and frequent fluctuations in BP also pose a significant impediment to effective treatment in the SCI population.

Individuals with high cord lesions paradoxically struggle with chronic hypotension and OH as well as significant life threatening and unpredictable increases in BP during episodes of AD. [97, 98] Further, although AD may be associated with symptoms such as headache, pounding in the ears and head, sweating below the lesion level, silent AD has been reported and can lead to cerebral hemorrhage [99, 100] and even death. [19, 101] The lack of rigorous clinical trials aimed at identifying the impact of anti-hypotensive treatment on BP increases during AD warrants restraint in treatment to normalize BP in the SCI population. However, increases in BP with midodrine during sexual stimulation to promote ejaculation, did not significantly heighten the BP response compared to no-drug. [20] Midodrine is the only anti-hypotensive agent that has been tested on the BP response to AD, which is an alpha-agonist that binds to vascular alpha receptors causing vasoconstriction and increased BP. Because of direct alpha receptor binding, midodrine may, if tested more rigorously, increases BP during a bout with AD. In contrast, droxidopa is a prodrug that is converted to NE, stored primarily in non-neuronal tissue and is released upon stimulation of the post-ganglionic sympathetic neurons during an

orthostatic provocation. [17] Because droxidopa is a prodrug and is not bound to the alpha receptors, exacerbation of the BP elevations during AD seems less likely, but this has not been tested.

Anti-Hypotensive Treatment in SCI:

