Screening Visit – Individuals with SCI will be approached by investigators and asked to provide informed consent to participate in a screening study to determine eligibility. Compression garments will be removed, if tolerated, prior to assessment of supine and seated BP.

Any subject taking a vasoconstrictor agent will be asked to stop these medications 2 days or 5 half-lives (whichever is longer) prior to the screening visit, if medically cleared. The screening assessments will include: medical intake information (Appendix 1), medical history (Appendix 2), physical examination, American Spinal Cord Injury Impairment Scale (AIS) classification (if not assessed in the prior 6-months), clinical symptoms survey for OH and AD (Appendix 3) and

brachial BP assessment, recorded one time per minute for 10 minutes while in the seated and supine positions. Individuals will be eligible to participate in the study if 1) the average seated BP meets the WHO definition of hypotension (i.e., SBP \leq 110 mmHg for males or SBP \leq 100 mmHg for females) or 2) there is evidence of OH (i.e., orthostatic fall in BP \geq 20/10 mmHg when moved from the supine to the seated position) and 3) there is no evidence of sustained elevation in BP \geq 140/100 mmHg in either the supine or seated positions. This visit will take about 2 hours.

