Study 1– To determine the proportion of subjects with SCI with: 1.1) a normotensive response to droxidopa and 1.2) a sustained hypertensive response to droxidopa. The dose optimization study will be scheduled to begin after completion of the screening visit. Eligible participants will be administered oral droxidopa in a dose escalation, open-label manner beginning with 200 mg. The dose will be adjusted upwards by 100 mg on subsequent visits until (1) average SBP recorded 60-120 minutes after dose administration is 111-139 mmHg in males and 101-139 mmHg in females (i.e., normotensive), (2) sustained elevation (\geq 30 consecutive minutes) in seated SBP \geq 140/100 mmHg, (3) maximum dose of 800 mg is reached without adequate SBP response or (4) intolerable side effects considered related to study medication. Subjects will visit the testing laboratory on as few as 1 (200 mg) and as many as 8 (800 mg) days, and will be asked to refrain from taking prescription anti-hypotensive agents for 12 hours prior to study. Participants with an excessive response to the 200mg dose, i.e., average 4-hour SBP above 139, will be asked to visit the laboratory to determine their blood pressure response to a 100mg dose. Based on our previous data, we do not anticipate an excessive response to the 200mg dose in most participants, we request the addition of the 100mg dose be administered only in participants with excessive responses to the 200mg dose. Subsequent study visits will be scheduled no less than 2 and no more than 10 days apart. Subjects will arrive at the laboratory between 10AM and 1PM after a light breakfast and having avoided alcohol, caffeine, and nicotine for 12-hours. Subjects will remain in their wheelchair for instrumentation, which will include: 1) 3-lead electrocardiogram (ECG) for continuous recording of heart rate (HR) and respiration rate; 2) brachial BP, which will be monitored using a manual sphygmomanometer and finger arteriolar beat-to-beat BP, which will be recorded using photoplethysmography with a cuff placed around the middle or index finger of the left hand. Seated cardiovascular hemodynamic assessments will be monitored and recorded at 15-minute intervals for 4-hours, and the side effects questionnaire (Appendix 4) will be administered hourly during the 4-hour study. Individuals who do not respond to droxidopa with a normal seated SBP will be excluded from Study 2. Each study visit will take about 5 hours.

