- **Cerebral Blood Flow Velocity** – will be monitored using Transcranial Doppler (TCD) ultrasound (Terumo Cardiovascular Systems [name]) to assess blood flow velocity (cm/s) at the left middle cerebral artery (MCA) through the temporal window. The MCA signature will be identified by the depth (45-55 mm), sound and direction of flow (towards the probe), as evidenced by the color and spectral waveform. The TCD probe will be operated at a frequency of 2.0 MHz to visualize the MCA through the temporal window; once visualized, a head-harness will be used to secure probe placement for the duration of testing. TCD recordings of CBFv will be viewed in real-time continuously throughout testing and will be recorded at intervals described above. The raw analog CBFv signal will be digitized and stored for subsequent analysis using customized programs created with LabView graphical software.

Blood Draws:

- Four plasma samples (20 mL per sample) will be drawn from an antecubital vein for analysis of changes in plasma renin, serum aldosterone and plasma norepinephrine concentrations following administration of droxidopa compared to placebo. Concentration of these vasoactive substances are altered during orthostatic provocation, which may be differentially affected by study drug compared to placebo.

Surveys

- **Vancouver Coastal Health Autonomic Dysfunction following SCI Survey** (Appendix 3) - will be used to determine the frequency and severity of the common symptoms and side effects of AD and OH.
- **Side-Effects Survey** (Appendix 4) – The most common side-effects reported with droxidopa are headache (%) dizziness (%) nausea (%) hypertension (%) and fatigue. In addition, subjects may report: feeling feverish, muscle cramps, confusion and uncontrolled movements. Therefore, we will ask participants questions related to these known side-effects and will gather data on any other subject symptom that may be related to the study medication.
- **The Visual Analog Fatigue Scale** (Appendix 5) – will be used one time per study visit to determine the effects of droxidopa dose (Study 1) compared to placebo (Study 2) on self-report severity of fatigue.

Data Analysis:

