Because Study 2 is a randomized blinded placebo controlled trial we have included a data safety monitor to review individual blood pressure responses and trends in hemodynamic and symptoms in aggregate data. [name], MD will be an independent clinical monitor, he will have a copy of the randomization code and will contact study investigators if a concern arises pertaining to a study participant and will be in contact with the participant who may be experiencing increased symptoms related to AD.

Home Monitoring: Participants will be monitored for 4 hours or until their blood pressure has returned to baseline levels ($\pm 10/5$ mmHg). No subject will be sent home with a blood pressure that is elevated above 140/90 mmHg. However, if blood pressure remains above their baseline, **but not in the hypertensive range**, after 4-hours of testing they may be sent home with a 24-hour blood pressure monitor, which will be programmed to obtain a blood pressure reading every 20 minutes during the day and at 30-minute intervals during the night. The study coordinator or the PI will follow-up by phone with the subject to asses any adverse side effects and to document blood pressure changes. The subject will be asked to immediately report any significant AE they may feel after leaving the laboratory.

Literature Cited

1. Claydon, V.E. and A.V. Krassioukov, *Orthostatic hypotension and autonomic pathways after spinal cord injury*. J Neurotrauma, 2006. **23**(12): p. 1713-25.
2. Guttmann, L., et al., *Effect of Tilting on the Cardiovascular Responses and Plasma Catecholamine Levels in Spinal Man*. Paraplegia, 1963. **1**: p. 4-18.
3. Mathias, C.J., et al., *Plasma catecholamines, plasma renin activity and plasma aldosterone in tetraplegic man, horizontal and tilted*. Clin Sci Mol Med, 1975. **49**(4): p. 291-9.
4. Wecht, J.M., et al., *Direct and reflexive effects of nitric oxide synthase inhibition on blood pressure*. Am J Physiol Heart Circ Physiol, 2008. **294**(1): p. H190-7.
5. Wecht, J.M., et al., *A prospective report on the prevalence of heart rate and blood pressure abnormalities in veterans with spinal cord injuries*. J Spinal Cord Med, 2013. **36**(5): p. 454-62.
6. Zhu, C., et al., *A retrospective chart review of heart rate and blood pressure abnormalities in veterans with spinal cord injury*. J Spinal Cord Med, 2013. **36**(5): p. 463-75.

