IND number or other status (submit validation or correspondence): **137213**

If there is no IND number, is there an FDA exemption? (If yes, please submit FDA correspondence.)? **See attached FDA IND letter.**

YES	X	NO	
-----	---	----	--

d. Will investigational devices be used:

No.

Is there an IDE issued by the FDA? **N/A**

YES		NO	
-----	--	----	--

IDE number or other status (submit validation or correspondence):

Is there an abbreviated IDE?

YES		NO	
-----	--	----	--

If there is no IDE number, is there an FDA exemption? (If yes, please submit correspondence with FDA.)?

YES		NO	
-----	--	----	--

How would you determine the risk-benefit analysis for investigational devices?

e. Risks for Investigational Drugs/Device:

For investigational drugs, what are the possible risks associated with the study drug relative to possible interactions with medications likely to be used by subjects? **Following droxidopa, administration BP may elevate above the normal range (>140/90 mmHg). In addition, symptoms of autonomic dysreflexia (AD) may become frequent or worsen while taking the study medication. Clinical staff will assist the subject to an upright seated position, loosen any tight clothing or braces that the subject is wearing and may check and empty your bladder and bowel. If BP remains high for more than 30 minutes the subject will be provided with a medication to lower their pressure. The medication of choice will be a nitropaste (Nitroglycerin Ointment, 2%) that will be placed one inch on the subjects forehead.**

Droxidopa risks ($\leq 8\%$ likely) include: slow or fast heartbeat, pounding in the ears, low back or side pain, and nervousness.

Since this research may have unknown effects on an unborn child and should not be done during pregnancy, it is necessary for a pregnancy test to be done first. To your knowledge you are not pregnant at the present time. You also agree to avoid becoming pregnant (use contraceptives, take precautions against becoming pregnant, etc.) during this study.

As with any research, there may be unforeseen risks and discomforts. A medical doctor associated with the study will be available to treat any medical emergency that may develop.

What will your approach be to such risks? **Study personnel and clinical staff will monitor BP daily during the study participation period.**

Will such subjects be excluded from the study? **No.**

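### Worse autonomic dysreflexia is a named droxidopa risk, but its survey is scheduled only at screening and no analysis reports its symptoms by dose or against placebo

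*Combined protocol and SAP*

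**What the plan says.** **The risk.** Item 15.e of the Combined protocol and SAP warns that "symptoms of autonomic dysreflexia (AD) may become frequent or worsen while taking the study medication". The Protocol's background on hypotension in SCI expects less trouble from droxidopa than from midodrine, but concedes the evidence gap: "exacerbation of the BP elevations during AD seems less likely, but this has not been tested". The same section describes how AD presents: "headache, pounding in the ears and head, sweating below the lesion level, silent AD has been reported".

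**The monitor's task.** Under Safety Monitoring, the independent clinical monitor for Study 2 holds the randomisation code, reviews BP responses and symptoms, and "will be in contact with the participant who may be experiencing increased symptoms related to AD".

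**The instruments.** The Surveys section says the Vancouver AD survey (Appendix 3) "will be used to determine the frequency and severity of the common symptoms and side effects of AD and OH". The Procedures Table, as it reads in the supplied text, marks it at screening only, and the Screening Visit text agrees. On drug, symptoms are taken with the general side-effects form (Appendix 4). In Study 1, "the side effects questionnaire (Appendix 4) will be administered hourly during the 4-hour study"; in Study 2 it is given after the tilt. The Surveys description of that form names headache among the known droxidopa effects and adds that staff "will gather data on any other subject symptom that may be related to the study medication". It does not name AD.

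**The analysis.** Hypotheses 1.1 to 2.4 (Protocol, Data Analysis; Combined protocol and SAP, item 17.a) contain no AD result.

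**The concern.** The plan names a risk specific to this population and gives the monitor a duty tied to it, but specifies no on-drug measure of that risk and no summary of it. Without a prompt, an AD episode may be written down as a headache, entered as free text, or not mentioned. A symptom that was never asked about cannot be recovered at analysis.

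The pilot is meant to help plan a larger trial of utility and safety. The Protocol's Significance section says that AD justifiably holds clinicians back from treating hypotension in these patients. A count of AD symptoms by dose and against placebo is therefore something the later trial would want, and as written the pilot is not set up to supply one.

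**Working it through.** The documents give no AD rate, so there is no figure of the plan's own to reproduce. The check is a comparison of sections, followed by a calculation of what the missing table could show.

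**1. Where AD is measured.**
- Procedures Table: one mark for the AD survey, at screening. Other rows (side effects, fatigue, supine BP) carry marks at later visits, so the single mark does not look like a reading error.
- Screening Visit text: the Appendix 3 survey is listed among the screening assessments.
- Combined protocol and SAP, item 13.b: an OH questionnaire at all visits and no AD instrument.

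**2. Where AD could enter an analysis.**
- Hypothesis 1.2 pools sustained hypertension with intolerable drug-related side effects into one proportion. AD symptoms that are tolerable, without sustained hypertension, do not count, and there is no split by dose.
- Hypothesis 2.1B compares supine BP readings at or above 140/100 mmHg between conditions. It includes no symptoms.
- No other hypothesis concerns symptoms.

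**3. How often the form is already given.** Study 1 runs from 200 to 800 mg in 100 mg steps, which is 7 doses. At 4 hourly forms per visit, 7 × 4 = 28 forms at most per participant. Study 1 has 40 participants in the Protocol and 60 in the Combined protocol and SAP; Study 2 has 25 and 30.

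**4. What a paired Study 2 table could show.** Suppose, for illustration, that 3 participants report symptoms on droxidopa and none on placebo. The Newcombe paired score interval gives:

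| n | Difference | 95% CI |
|---|---|---|
| 25 | 3/25 = 12.0% | -3.5% to 30.0% |
| 30 | 3/30 = 10.0% | -3.1% to 25.6% |

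Exact McNemar, two-sided, with all discordant pairs in one direction: p = 2 × 0.5^k. Five pairs give 0.0625 and six give 0.031. Six participants are 6/25 = 24% or 6/30 = 20%, so only a large imbalance would reach significance.

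**5. What the Study 1 dose table could show.** Responders stop escalating, so numbers fall as dose rises. If only those who never normalise reach 800 mg (assumption), that dose has 40 - 25 = 15 participants, or 60 × (1 - 0.60) = 24. They are selected by non-response, so doses cannot be compared as if randomised.

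**6. Participants at risk.** Any injury level is eligible, while the Significance section describes AD in injury above T6. The documents give no split. If half are above T6 (assumption), Study 2 has about 12 (25/2) to 15 (30/2) such participants.

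**The case against.** A reader might infer that AD goes unmonitored, or that AD symptoms go uncollected on drug. The documents do not support either reading.
- Frequent or severe AD is excluded (Combined protocol and SAP, item 7).
- BP above 140/90 mmHg for more than 30 minutes triggers action, and item 15.e sets out the response directly after naming the risk.
- Intolerable drug-related effects stop escalation and count in Hypothesis 1.2.
- Observation lasts 4 hours or until BP returns to baseline, with a possible 24-hour monitor and a telephone call.
- Item 16 adds frequent symptom questions, telephone follow-up, weekly adverse event review and monthly review of cumulative data.

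The form itself may be better than its description. Headache is already named, and item 15.e lists pounding in the ears as a droxidopa risk, so Appendix 4 may ask about it. Only sweating below the injury has no trace in the supplied account of on-drug questions. If the OH questionnaire in item 13.b is the combined Appendix 3 form, AD items are already repeated and only the tabulation is missing. These points stand, and they make the collection part of the fix conditional.

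It might also seem that participants should be asked about AD over the whole gap between visits. That would mostly count background AD. Doses are single and the half-life is 2 to 3 hours, so 10 days is at least 240/3 = 80 half-lives. The event-count exclusion starts above 3 symptomatic events a week, so someone at that limit could have about 3 × 10/7 ≈ 4 events in 10 days without drug.

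Nor do upper limits for zero events size the gap. With nobody affected among 25, the limit is 1 - 0.025^(1/25) = 13.7%, but zero reports are implausible when milder AD is eligible and headache is a common droxidopa effect.

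Finally, this is an unpowered pilot with no planned AD provocation, and it tabulates no individual side effect. That lowers the weight of the point. It does not remove it, because AD is the symptom complex that the plan singles out and assigns to the monitor.

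**Conclusion.** The point holds as a minor, cheap improvement. The plan names worse AD as a drug risk and gives the monitor an AD-specific duty, yet schedules the AD survey only before drug and specifies no summary of AD symptoms by dose or against placebo. On the reading most favourable to the plan, where Appendix 4 or a repeated Appendix 3 already holds the items, the missing summary remains.

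A reader might go further and conclude that the safety findings are invalid. They are not: Hypotheses 1.2 and 2.1B ask about hypertension, intolerable effects and supine BP, and no stated hypothesis becomes wrong without AD data. The loss is of descriptive safety information for the next trial, with intervals as wide as those shown above.

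This rests on the Procedures Table having been read correctly, which the screening text supports, and on the description of Appendix 4, since the form itself was not available.

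**What to change.** 1. Check Appendix 4. Where they are absent, add headache, pounding in the ears or head, and sweating below the injury as named items at every Study 1 and Study 2 dosing visit. Use identical prompts on droxidopa and placebo.
2. Record BP and clock time beside each positive report, and have the study physician judge whether it is AD, before unblinding in Study 2. Do not define AD by a BP rise alone, which cannot be told apart from the drug's pressor effect.
3. Tabulate participants with these symptoms and participants with physician-judged AD: descriptively by dose in Study 1, with the number dosed at each level, and as a paired droxidopa-versus-placebo difference with a 95% CI in Study 2. Show both overall and for injury above T6, and give the table to the monitor.
4. Limit any question after the visit to the rest of the dosing day, asked through the existing follow-up call.

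**Cost.** At an assumed 10 seconds per item, 3 items × 10 s × 4 forms = 120 s, or 2 minutes, per Study 1 visit, and less if Appendix 4 already covers some items. There is also a brief physician judgement for each positive report, and one table. No new staff, visit or procedure is needed.

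**Downside.** The symptoms are not specific to AD, prompting may raise reports in both Study 2 conditions, silent AD will be missed, and the intervals are wide. The report should say that the table is descriptive only.
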